## 12.2 Analysis Sets

The following analysis sets are defined: All Subjects Set, Full Analysis Set (FAS), and Safety Set. Additional analysis sets related to the Run-in Period will be defined in the SAP, as appropriate.

The **All Subjects Set** will include all subjects who were randomized or received at least 1 dose of study drug. This analysis set will be used for all individual subject data listings and disposition summary tables, unless otherwise specified.

The **FAS** will include all randomized subjects who carry the intended *CFTR* allele mutation and receive at least 1 dose of study drug in the Treatment Period. The FAS will be used to summarize subject demographics and baseline characteristics, and for all efficacy analyses in which subjects will be analyzed according to their randomized treatment group, unless otherwise specified.

The **Safety Set for the Treatment Period** will include all subjects who receive at least 1 dose of study drug in the Treatment Period. This safety set will be used for all safety analyses in which subjects will be analyzed according to the treatment they receive, unless otherwise specified.

The **Safety Set for the Run-in Period** will include all subjects who received at least 1 dose of study drug in the Run-in Period.

## 12.3 Statistical Analysis

### 12.3.1 General Considerations

**Continuous variables** will be summarized using the following descriptive summary statistics: the number of subjects (n), mean, SD, median, minimum value (min), and maximum value (max).

**Categorical variables** will be summarized using counts and percentages.

The **baseline value**, unless otherwise specified, will be defined as the most recent non-missing measurement (scheduled or unscheduled) collected before the first dose of study drug in the Treatment Period (i.e., the Day 1 Visit). For ECG, baseline will be defined as the most recent pretreatment measurement (or the average of triplicate measurements, if the most recent pretreatment measurement is obtained in triplicate) before the first dose of study drug in the Treatment Period (i.e., the Day 1 Visit).

**Absolute change** from baseline will be calculated as post-baseline value – baseline value.

The **Treatment-emergent (TE) Period for the Run-in Period** will be from the first dose of study drug in the Run-in Period to (1) the first dose of study drug in the Treatment Period for subjects who complete the Run-in Period and continue to the Treatment Period, or (2) 28 days

after the last dose date of study drug in the Run-in Period for subjects who do not continue to the Treatment Period (e.g., subjects who do not meet the conditions to enter the Treatment Period).

The **TE Period for the Treatment Period** will include the time from the first dose date of study drug in the Treatment Period (VX-445/TEZ/IVA or placebo + TEZ/IVA) to 28 days after the last dose of the study drug or to the completion of study participation date (as defined in Section 9.1.7), whichever occurs first.

### **12.3.2 Background Characteristics**

#### **12.3.2.1 Subject Disposition**

The number and percentage of subjects in each disposition category (e.g., randomized, included in the FAS, included in the Safety Set, completed Treatment Period, completed study, prematurely discontinued treatment or study with a breakdown of the reasons for discontinuation, and entered an open-label study) will be summarized overall and by treatment group.

An additional subject disposition summary related to the TEZ/IVA Run-in Period will be defined in the SAP, as appropriate.

#### **12.3.2.2 Demographics and Baseline Characteristics**

Demographic, medical history, and baseline characteristics will be summarized using descriptive summary statistics.

The following demographics and baseline characteristics will be summarized overall and by treatment group for the FAS, and will include (but are not limited to): sex, race, age, baseline weight, baseline height, baseline body mass index, baseline CFQ-R, baseline ppFEV1, and baseline SwCl.

Medical history will be summarized by MedDRA System Organ Class (SOC) and Preferred Term (PT) for the FAS.

#### **12.3.2.3 Prior and Concomitant Medications**

Medications will be coded using the World Health Organization Drug-Dictionary and categorized as follows:

- **Prior medication:** any medication that was administered during the 56 days before the first dose of study drug in the Treatment Period but not in the Run-in Period. For subjects who discontinue during the Run-in Period and whose first dose of study drug in the Treatment Period is not available, prior medication will be any medication that was administered during the 56 days before the last dose of study drug in the Run-in Period but before the first dose in the Run-in Period
- **Concomitant medication during the Run-in Period:** medication continued or newly received during the TE Period for the Run-in Period
- **Concomitant medication during the Treatment Period:** medication continued or newly received during the TE Period for the Treatment Period
- **Post-treatment medication:** medication continued or newly received after:

- the TE Period for the Run-in Period if the subject did not receive study drug in the Treatment Period
- the TE Period for the Treatment Period for subjects who received study drug in the Treatment Period

A given medication may be classified as a prior medication, a concomitant medication, or a post-treatment medication; both prior and concomitant; both concomitant and post-treatment; or prior, concomitant, and post-treatment. If a medication has a missing or partially missing start/end date or time and if it cannot be determined whether it was taken before the first dose of study drug, concomitantly during the TE Period, or after the TE Period, it will be considered in all 3 categories of prior, concomitant, and post-treatment medication.

Prior medications and concomitant medications will be summarized descriptively by Preferred Name based on the FAS. Post-treatment medications will be provided separately in an individual subject data listing.

#### **12.3.2.4 Study Drug Exposure and Compliance**

Study drug exposure and compliance will be summarized for the Treatment Period only.

Study drug exposure will be summarized overall and by treatment group, based on the Safety Set in terms of the duration of treatment a subject received (in days), defined as the last day – the first day of study drug plus 1, regardless of study drug interruption.

Study drug compliance will be summarized overall and by treatment group based on the FAS, and will be calculated as:  $100 \times [1 - (\text{total number of days of study drug interruption}) / (\text{duration of study drug exposure in days})]$ . A study drug interruption on a given day is defined as an interruption of any study drug on that day.

#### **12.3.2.5 Important Protocol Deviations**

An important protocol deviation (IPD) is a deviation that may significantly affect the completeness, accuracy, or reliability of the study data or that may significantly affect a subject's rights, safety, or well-being. The rules for identifying an IPD will be described in the SAP.

All IPDs will be provided in an individual subject data listing and summarized, as appropriate.

### **12.3.3 Efficacy and Pharmacodynamic Analyses**

The primary objective of the study is the evaluation of the efficacy of VX-445/TEZ/IVA. The analysis in this section will be based on the FAS, unless otherwise specified.

#### **12.3.3.1 Analysis of Primary Endpoint**

The primary efficacy endpoint is the **absolute change in CFQ-R respiratory domain score from baseline through Week 24**. The analysis of this endpoint will be performed using a mixed-effects model for repeated measures (MMRM) with absolute change from baseline in CFQ-R respiratory domain score at each post-baseline visit as the dependent variable. The model will include treatment group, visit, and treatment-by-visit interaction as fixed effects, and will be adjusted for selected covariates as appropriate. Details will be described in the SAP. The model will be estimated using restricted maximum likelihood. Denominator degrees of freedom for the F test for fixed effects will be estimated using the Kenward-Roger approximation. An unstructured covariance structure will be used to model the within-subject errors. If the model

estimation does not converge, a compound symmetry covariance structure will be used instead. Conditional on the observed data and covariates, missing data will be assumed to be missing at random; consequently, no imputation of missing data will be performed.

The primary result obtained from the model will be the estimated treatment difference through Week 24 (defined as the average of Weeks 4, 8, 16, 24). The least squares (LS) mean estimate with a 2-sided 95% CI and a 2-sided  $P$  value will be provided. The treatment difference at each post-baseline visit, obtained from the model, will also be provided.

Additional [REDACTED] or subgroup analyses if appropriate will be described in the SAP.

### **12.3.3.2 Analysis of Key Secondary Endpoint**

- **Absolute change in ppFEV1 from baseline through Week 24**

The analysis of this endpoint will be based on an MMRM model similar to the CFQ-R endpoint above, with absolute change from baseline in ppFEV1 at each post-baseline visit as the dependent variable.

The primary result obtained from the model will be the estimated treatment difference through Week 24 (defined as the average of Weeks 4, 8, 16, 24). Data obtained from the Day 15, Week 4, Week 8, Week 16, and Week 24 Visits will be included in the model. The Day 15 Visit will not be included in the estimation of the average treatment effect through Week 24. The LS mean estimate with a 2-sided 95% CI and a 2-sided  $P$  value will be provided. The treatment difference at each post-baseline visit, obtained from the model, will also be provided.

### **12.3.3.3 Analysis of Secondary Endpoint**

- **Absolute change in SwCI from baseline through Week 24**

The analysis of this endpoint will be based on an MMRM model similar to the analysis of the primary endpoints above, with absolute change from baseline in SwCI at each post-baseline visit as the dependent variable. Data obtained from Week 4, Week 8, and Week 24 Visits will be included in the model and all of these visits will be included in the estimation of the average treatment effect through Week 24. The treatment difference at each post-baseline visit, obtained from the model will also be provided.

### **12.3.3.4 Multiplicity Adjustment**

A hierarchical fixed-sequence testing procedure will be used to control the overall family-wise type I error at a 2-sided alpha of 0.05 for the testing of the primary endpoint and key secondary endpoints. The testing order is as follows:

1. Primary endpoint: Absolute change in CFQ-R respiratory domain score from baseline through Week 24
2. Key secondary endpoint: Absolute change in ppFEV1 from baseline through Week 24

For a test at any step to be considered statistically significant within the testing hierarchy, it must be statistically significant, and all previous tests (if any) within the hierarchy must be statistically significant. In other words, the key secondary endpoint (ppFEV1) will only be tested if the primary endpoint is statistically significant.

### 12.3.4 Safety Analysis

All safety analyses will be based on data from the TE Period for all subjects in the Safety Set. The overall safety profile of study drug will be assessed based on the following safety and tolerability endpoints:

- Treatment-emergent adverse events (TEAEs)
- Clinical laboratory values (i.e., hematology, serum chemistry, coagulation, and urinalysis)
- ECGs
- Vital signs
- Pulse oximetry

All safety data from the TE Period will be summarized by treatment group, unless otherwise specified.

All safety data will be presented in individual subject data listings, including safety data from the Run-in Period.

#### 12.3.4.1 Adverse Events

For analysis purposes, AEs will be classified as pretreatment AEs, TEAEs during the Run-in Period, TEAEs during the Treatment Period, or post-treatment AEs, defined as follows:

- **Pretreatment AE:** any AE that occurred before the first dose date of study drug (TEZ/IVA) in the Run-in Period
- **TEAE during the Run-in Period:** any AE that worsened (either in severity or seriousness) or that was newly developed at or after the first dose date of study drug (TEZ/IVA) through the end of the TE Period for the Run-in Period
- **TEAE during the Treatment Period:** any AE that worsened (either in severity or seriousness) or that was newly developed at or after the first dose date of study drug (TC or placebo + TEZ/IVA) in the Treatment Period through the end of the TE Period for the Treatment Period
- **Post-treatment AE:** any AE that worsened (either in severity or seriousness) or that was newly developed after:
  - the TE Period for the Run-in Period if the subject did not receive treatment in the Treatment Period
  - the TE Period for the Treatment Period if the subject received treatment in the Treatment Period

For AEs with missing or partial start dates, if there is no clear evidence that the AEs started before or after study drug treatment, then the AEs will be classified as TEAEs corresponding to the Treatment Period.

Unless otherwise specified, TEAE refers to TEAE during the Treatment Period.

AE summary tables will be presented by treatment group, and will include the following:

- Overview of TEAEs

- TEAEs
- Related TEAEs
- TEAEs by maximum severity
- Grade 3/4 TEAEs
- Serious TEAEs
- Related serious TEAEs
- AE of special interest (details will be described in SAP)
- TEAEs leading to treatment discontinuation
- TEAEs leading to treatment interruption

Summaries will be presented by MedDRA SOC and PT using frequency counts and percentages (i.e., number and percentage of subjects with an event). When summarizing the number and percentage of subjects with an event, subjects with multiple occurrences of the same AE or a continuing AE will be counted once, only the maximum severity level will be presented in the severity summaries, and the strongest relationship level in the relationship summaries.

Listings containing individual subject level AE data will be provided separately for:

- Serious TEAEs
- TEAEs leading to treatment discontinuation
- TEAEs leading to treatment interruption
- TEAEs leading to death

In addition, all AEs, including pre- and post-treatment AEs, will be presented in individual subject data listings.

#### **12.3.4.2 Clinical Laboratory Assessments**

For the treatment-emergent laboratory measurements, the observed values and change from baseline values of the continuous hematology, serum chemistry, and coagulation results will be summarized in SI units by treatment group at each visit.

The number and percentage of subjects with at least 1 threshold analysis event during the TE Period will be summarized by treatment group. The threshold analysis criterion shift from baseline will also be summarized for select laboratory parameters. The threshold analysis criteria and the parameter selection criteria will be provided in the SAP.

Results of urinalysis and pregnancy tests will be listed in individual subject data listings only. In addition, a listing containing individual subject hematology, chemistry, and coagulation values will be provided. This listing will include data from scheduled and unscheduled visits.

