## 8.2 Exclusion Criteria

1. History of any illness or any clinical condition that, in the opinion of the investigator, might confound the results of the study or pose an additional risk in administering study drug(s) to the subject. This includes, but is not limited to, the following:
  - Clinically significant cirrhosis with or without portal hypertension.
  - Solid organ or hematological transplantation.
  - Alcohol or drug abuse in the past year, including, but not limited to, cannabis, cocaine, and opiates, as deemed by the investigator.
  - Cancer, except for squamous cell skin cancer, basal cell skin cancer, and Stage 0 cervical carcinoma in situ (all 3 having occurred more than 5 years before screening with no recurrence for the last 5 years).
2. Any of the following abnormal laboratory values at screening:
  - Hemoglobin  $< 10$  g/dL
  - Total bilirubin  $\geq 2 \times$  upper limit of normal (ULN)
  - Aspartate transaminase (AST), alanine transaminase (ALT), gamma-glutamyl transferase (GGT), or alkaline phosphatase (ALP)  $\geq 3 \times$  ULN
  - Abnormal renal function defined as glomerular filtration rate  $\leq 50$  mL/min/1.73 m^2 (calculated by the Modification of Diet in Renal Disease Study Equation) for subjects  $\geq 18$  years of age and  $\leq 45$  mL/min/1.73 m^2 (calculated by the Counahan-Barratt equation) for subjects aged 12 to 17 years (inclusive)
3. An acute upper or lower respiratory infection, pulmonary exacerbation(s) (PEX), or changes in therapy (including antibiotics) for sinopulmonary disease within 28 days before the first dose of TEZ/IVA in the Run-in Period (Day -28).
4. Lung infection with organisms associated with a more rapid decline in pulmonary status (including, but not limited to, *Burkholderia cenocepacia*, *Burkholderia dolosa*, and *Mycobacterium abscessus*). For subjects who have had a history of a positive culture, the

investigator will apply the following criteria to establish whether the subject is free of infection with such organisms:

[figure not shown]
- The subject has not had a respiratory tract culture positive for these organisms within the 12 months before the date of informed consent.

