  - IVA is a weak inhibitor of P-glycoprotein (P-gp). Administration of IVA may increase systemic exposure of medicinal products that are sensitive substrates of P-gp, which may increase or prolong their therapeutic effect and adverse reactions. Digoxin or other substrates of P-gp with a narrow therapeutic index, such as cyclosporine, everolimus, sirolimus, and tacrolimus, should be used with caution and appropriate monitoring.
  - IVA may inhibit CYP2C9; therefore during coadministration with warfarin, additional monitoring of the international normalized ratio is recommended. Other medicinal products that are CYP2C9 substrates for which exposure may be increased include glimepiride and glipizide; these should be used with caution.
  - Information about bronchodilator use during the study will be collected and documented. Subjects who are using a bronchodilator must have their spirometry assessments performed according to the guidelines provided in Section [11.4.2](#).

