9.4.2 Clinical Laboratory

For the treatment emergent laboratory measurements, the observed values and change from baseline values of the continuous hematology, serum chemistry, and coagulation results will be summarized in SI units by treatment group at each visit.

The number and percentage of subjects meeting at least 1 threshold analysis criterion, during the TE period for Treatment Period, will be summarized by treatment group. The threshold analysis of shift from baseline will also be summarized for LFT laboratory parameters. The threshold analysis criteria are provided in [Appendix E](#).

For selected LFT laboratory tests (alanine transaminase [ALT], aspartate transaminase [AST], alkaline phosphatase [ALP], and total bilirubin), a scatter plot of the maximum treatment-emergent value versus the baseline value corresponding to \times ULN (upper limit of normal) will be

presented by treatment group. Further, a scatter plot of the maximum treatment-emergent value of ALT and AST, separately, versus the maximum treatment-emergent value of total bilirubin corresponding to \times ULN will also be presented by treatment group.

Results of urinalysis and positive urine/serum pregnancy test will be listed in individual subject data listings only. For positive serum pregnancy listing, subjects with serum HCG which are abnormally high will be selected.

In addition, a listing containing individual subject hematology, chemistry, and coagulation values will be provided. This listing will include data from both scheduled and unscheduled visits.

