Appendix E: Criteria for Threshold Analysis

Table 12-3 Threshold Analysis Criteria for Laboratory Tests (as applicable)

Parameter	Threshold Analysis	Comments
Clinical Chemistry (LFT)		
ALT	>ULN - ≤3xULN >3x - ≤ 5xULN >5x - ≤ 8xULN >8x - ≤ 20.0xULN >20.0xULN	FDA DILI Guidance Jul 2009.
AST	>ULN - ≤3xULN >3x - ≤ 5xULN >5x - ≤ 8xULN >8x - ≤ 20.0xULN >20.0xULN	FDA DILI Guidance Jul 2009.
ALT or AST	(ALT>ULN - ≤ 3xULN) or (AST>ULN - ≤ 3xULN) (ALT>3x - ≤ 5xULN) or (AST>3x - ≤ 5xULN) (ALT>5x - ≤ 8xULN) or (AST>5x - ≤ 8xULN) (ALT>8x - ≤ 20xULN) or (AST>8x - ≤ 20xULN) ALT>20xULN or AST> 20 xULN	FDA DILI Guidance
Alkaline Phosphatase	>ULN - ≤ 1.5xULN >1.5 - ≤ 2.5 xULN >2.5 - ≤ 5.0 x ULN >5.0 - ≤ 20.0 x ULN >20.0 x ULN	FDA DILI Guidance Jul 2009.
Total Bilirubin	>ULN - ≤ 1.5xULN >1.5 - ≤ 2xULN >2 - ≤ 3xULN >3 - ≤ 10xULN >10xULN	FDA DILI Guidance Jul 2009.
Direct Bilirubin	>ULN - ≤ 1.5xULN >1.5 - ≤ 2xULN >2 - ≤ 3xULN >3 - ≤ 10xULN >10xULN	FDA DILI Guidance Jul 2009.
Indirect Bilirubin	>ULN - ≤ 1.5xULN >1.5 - ≤ 2xULN >2 - ≤ 3xULN >3 - ≤ 10xULN >10xULN	FDA DILI Guidance Jul 2009.
ALT and Total Bilirubin	ALT>3xULN and TBILI>2xULN	FDA DILI Guidance Jul 2009.

Table 12-3 Threshold Analysis Criteria for Laboratory Tests (as applicable)

Parameter	Threshold Analysis	Comments
AST and Total Bilirubin	AST>3xULN and TBILI>2xULN	FDA DILI Guidance Jul 2009.
(ALT or AST) and Total Bilirubin	(ALT>3xULN or AST>3xULN) and TBILI>2xULN	FDA DILI Guidance Jul 2009.
GGT	>ULN - ≤ 2.5xULN >2.5 - ≤ 5.0xULN >5.0 - ≤ 20.0xULN >20.0xULN	CTCAE grade 1-4
Clinical Chemistry (NON-LFT)		
Albumin	<LLN - ≥ 30 g/L <30 - ≥ 20 g/L <20 g/L	CTCAE grade 1-3
Amylase	>1x - ≤ 1.5xULN >1.5x - ≤ 2xULN >2x - ≤ 5xULN >5xULN	Criteria based upon CTCAE
Creatinine	>ULN - ≤ 1.5xULN >1.5 - ≤ 3.0xULN >3.0 - ≤ 6.0xULN >6.0xULN	CTCAE grades 1-4
Lipase	>ULN - ≤ 1.5xULN >1.5x - ≤ 2xULN >2x - ≤ 5xULN >5xULN	Criteria based upon CTCAE
Total protein	<LLN >ULN	No CTCAE
Creatine kinase	>ULN - ≤ 2.5 x ULN >2.5 - ≤ 5 x ULN >5 - ≤ 10x ULN >10 x ULN	CTCAE grades 1-4
Hematology		
Hemoglobin	Hgb decreased (anemia) <LLN - ≥ 100 g/L <100 - ≥ 80 g/L < 80 g/L	CTCAE grade 1-3
	Hgb increased >ULN - ≤ 20 g/L above ULN >20 g/L above ULN - ≤ 40 g/L above ULN >40 g/L above ULN	CTCAE grade 1-3

Table 12-3 Threshold Analysis Criteria for Laboratory Tests (as applicable)

Parameter	Threshold Analysis	Comments

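### Non-LFT laboratory threshold counts mix stable pre-existing abnormalities with new ones, because the count ignores baseline and only LFTs get a shift summary (minor).

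*Protocol*

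**What the plan says.** **Counting rule.** Protocol 12.3.4.2: "The number and percentage of subjects with at least 1 threshold analysis event during the TE Period will be summarized by treatment group". SAP 9.4.2 matches it: "The number and percentage of subjects meeting at least 1 threshold analysis criterion, during the TE period for Treatment Period". Neither sets a condition on the baseline value.

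**Form of the criteria.** Every laboratory criterion in SAP Appendix E, Table 12-3, is an absolute range: a multiple of ULN, a value below LLN, or a fixed cut-off. None requires a normal baseline or a worsening.

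**Shift summary.** The protocol says: "The threshold analysis criterion shift from baseline will also be summarized for select laboratory parameters". It leaves the choice of parameters to the SAP, and SAP 9.4.2 makes it: "The threshold analysis of shift from baseline will also be summarized for LFT laboratory parameters". Eleven Table 12-3 parameters are left without a shift summary: albumin, amylase, creatinine, lipase, total protein, creatine kinase, hemoglobin, platelets, reticulocytes, activated PTT and PT/INR.

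**Other laboratory output.** SAP 9.4.2 also provides observed values and change from baseline by visit for the continuous hematology, chemistry and coagulation results, and listings of individual values.

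**Baseline.** It is the last measurement before the first Treatment Period dose (SAP 9.1), taken after a four-week TEZ/IVA run-in.

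**The concern.** The randomized contrast is the addition of VX-445 to TEZ/IVA, and the run-in exists to give a stable on-TEZ/IVA baseline. A threshold count that ignores this baseline puts an abnormality that predates randomization and does not change in the same cell as one that appears after randomization.

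Elsewhere the plan does use baseline for categorical safety output:

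- A Treatment Period TEAE must be new or worsened: "any AE that worsened (either in severity or seriousness) or that was newly developed at or after the first dose date of study drug".
- Many ECG and vital-sign criteria in Tables 12-4 and 12-5 include a change from baseline.
- Pulse oximetry has a shift from baseline to the lowest value (SAP 9.4.5).
- LFTs have the shift summary.

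The entry criteria leave room for subjects to start inside a band. Protocol 8.2 lists exclusions under "Any of the following abnormal laboratory values at screening". Hemoglobin is excluded only below 10 g/dL (100 g/L), so a subject between 100 g/L and LLN already meets the first anemia band. No limit is listed for creatine kinase, amylase, lipase, platelets or coagulation.

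At stake is how clearly a reader can see new non-LFT abnormalities by arm. Mean change by visit does not give that number, and listings do not tabulate it.

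**Working it through.** The plan states no figure for the laboratory threshold analysis, so there is none to reproduce. The arm size comes from Protocol 12.1: 142 / (1 − 0.10) = 157.8, rounded up to 158, and 158 / 2 = 79 per arm.

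**Inputs that are assumptions** (the documents give no laboratory rates):

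- q: share already abnormal at baseline, equal in both arms, 5% to 30%.
- p: new-onset rate among subjects not abnormal at baseline.
- r: share of baseline-abnormal subjects with an abnormal value again in the TE period, 1.0 or 0.8.

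**Formulas.**

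- Tabulated proportion in an arm = q·r + (1 − q)·p.
- Tabulated risk difference = (1 − q)·(p1 − p0), because the q·r term is equal in both arms and cancels.
- Tabulated ratio = [q·r + (1 − q)·p1] / [q·r + (1 − q)·p0]. This is closer to 1 than p1/p0 whenever q·r > 0.

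**Main illustration: p = 5% (TEZ/IVA) versus 15% (triple), true ratio 3.0, true difference 10 points.**

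| q | Tabulated, r = 1 | Difference | Ratio, r = 1 | Ratio, r = 0.8 |
|---|---|---|---|---|
| 10% | 14.5% vs 23.5% | 9.0 points | 1.62 | 1.72 |
| 20% | 24.0% vs 32.0% | 8.0 points | 1.33 | 1.40 |
| 30% | 33.5% vs 40.5% | 7.0 points | 1.21 | 1.25 |

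At q = 10% in subjects per arm:

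- Pre-existing in each arm: 0.10 × 79 = 7.9.
- New in TEZ/IVA: 0.90 × 79 × 0.05 = 3.6.
- New in triple: 0.90 × 79 × 0.15 = 10.7.
- The table shows about 11.5 versus 18.6, and the new cases cannot be separated from the rest.

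**Other assumed onset rates, r = 1, q = 5%, 10%, 20%, 30%.**

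- 3% versus 10% (true ratio 3.33): ratios 1.85, 1.50, 1.25, 1.15. The difference falls from 7.0 points to 6.65, 6.3, 5.6 and 4.9.
- 10% versus 20% (true ratio 2.00): ratios 1.66, 1.47, 1.29, 1.19.

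**Where it falls.** The calculation treats one abnormal category. Table 12-3 is mostly graded, and a subject who moves into a worse band appears in that band. The dilution therefore sits mainly in the mildest bands. For hemoglobin, values below 100 g/L are excluded at screening, so the two lower bands mostly reflect later worsening.

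**The case against.** The strongest case is that this is a reporting choice and not an error. The protocol allows shifts for a selection of parameters, and the SAP selects LFTs. That fits the plan's safety focus: transaminase rules in Protocol 9.8.1 and elevated transaminases as an event of special interest in SAP 9.4.1.1. This stands. A reader might infer that the SAP breaks a protocol commitment to shift tables, and it does not.

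Second, new or worsened findings are captured elsewhere. Protocol 11.5.2 and 13.1.1.2 require abnormal laboratory results judged clinically significant to be reported as adverse events, and the TEAE tables require new onset or worsening. This also stands. It would be wrong to conclude that important non-LFT deterioration goes unreported. What remains outside those tables is threshold crossing that the investigator does not judge clinically significant.

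Third, a reader might infer that the rule favours one arm. Randomization balances baseline abnormality in expectation, and the control arm shows the background rate. The effect is dilution and not bias toward either treatment.

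Fourth, the entry criteria are tighter than a look at hemoglobin alone suggests. The GFR exclusions in Protocol 8.2 also restrict creatinine. The recommendation in Protocol 9.5 on monitoring INR with warfarin shows that such subjects may enter, but not how many.

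Fifth, the sizes rest on assumed rates. The ratio also looks more dramatic than the difference, which loses only the fraction q. A loss of statistical significance would not be a fair complaint, because SAP 9.4 plans no safety tests.

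Two points survive these objections: the counting rule has no baseline condition, and no laboratory table gives the number newly above or below a non-LFT threshold by arm.

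**Conclusion.** The point holds as a minor one. For 11 non-LFT parameters the planned threshold table combines stable pre-existing abnormalities with new ones.

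The direction follows from the counting rule: wherever some subjects are abnormal at baseline and remain so, the risk difference is multiplied by (1 − q) and the ratio moves toward 1. The size is unknown. Under the main assumptions (5% versus 15% new onset, q of 10% to 30%, all baseline abnormalities persisting) the ratio is 1.62 to 1.21 instead of 3.0, and the difference is 9 to 7 points instead of 10. With 80% persisting, the ratios are 1.72 to 1.25. If few subjects are abnormal at baseline for a parameter, the effect there is negligible.

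That baseline-abnormal subjects are counted is the plain reading, since nothing excludes them, although neither document says so outright. Efficacy inference and error control are not affected.

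**What to change.** In SAP 9.4.2:

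1. Extend the shift table (baseline category by worst TE-period category) to the non-LFT parameters in Table 12-3. Tabulate low and high directions separately for hemoglobin, platelets, total protein and reticulocytes, where a single worst category is not defined.
2. Keep the existing unconditional count. Beside it, give the number and percentage of subjects whose worst TE-period category is worse than their baseline category. For each category, the denominator is the subjects not already in that or a worse category at baseline.
3. Treat a missing baseline as normal and flag it, in line with the grouping in SAP 9.4.5 for oximetry.

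The protocol leaves parameter selection to the SAP, so its text can stand. The data are already collected. The cost is SAP wording, programming and extra table output.
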